6.5 POOLING OF CENTRES

Given the low number of patients per centre and the primarily descriptive nature of the statistical analysis, separate analyses by centre are not meaningful and will not be performed.

6.6 HANDLING OF MISSING DATA AND OUTLIERS

6.6.1 Withdrawals

The reasons for withdrawal from treatment will be reported as indicated on the eCRF.

6.6.2 Efficacy data

Binary efficacy endpoints

The primary imputation approach for binary endpoints will be No Response Imputation (NRI) described below.

1. If a patient prematurely discontinues study medication administration for any reason, then all data subsequent to the discontinuation will be considered to be missing. The cut-off date to be used is the last dose of study medication administration + 4 weeks (including the extended time windows).
2. For endpoints which are measured at multiple visits, if there are data at visits both before and after the visit with a missing outcome, then impute as success (a responder) only if both neighbouring visits also represent a success (independent of whether the preceding and following observations were selected for analysis based on time windows described in [Section 6.7](#)).

For all patients with a missing visit outcome, it will be imputed as a failure to achieve a response (non-responder).

In addition, for all binary endpoints (i.e., endpoints that are either 1 (patient responded) or 0 (patient did not respond)), frequency tables with observed data will be presented.

Categorical efficacy endpoints with more than two outcomes

Some endpoints or their subscores are categorical with more than two potential outcomes (e.g., IGA, DLQI). As a general rule, imputation will only be applied on the complete score. In case a categorical subscore is analysed separately, no imputation will be applied (only observed data will be analysed).

Continuous efficacy endpoints

For efficacy endpoints which are continuous in nature, no imputation of missing data is planned. Only observed data will be used for analysis.

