2. V1 of this extension trial should be preferably performed during the EOS of the preceding BI 655130 parent trial. When the visits are performed on the same day duplicate procedures across studies are performed once during the EOS/V1. If these visits are not performed on the same day then all V1 procedures need to be performed at that visit. The only exception is Infection Testing which does not have to be repeated if performed at EOS of the parent trial and there is a <12 week gap from EOS of parent trial to V1 of this trial. Refer also to [Section 6.2.1](#)
3. After the individual patient's end of the trial the investigator should report only any cancers of new histology and exacerbations of existing cancer, study treatment related SAEs and study treatment related AESIs of which the investigator may become aware of and only via the BI SAE form. Refer to [Section 5.2.6.2.1](#).
4. All patients who receive at least one dose in the trial, including those who discontinue treatment prematurely, should complete the EOT visit as soon as possible and complete the EOS visit 16 weeks after the date of last trial drug administration.
5. Where possible, electrocardiogram (ECG) measurements should precede blood sampling and drug administration. Refer to [Section 5.2.4](#)
6. Body Surface Area (BSA) will be calculated from Part A of the SCORAD. All assessments must be done prior to trial drug administration. The questionnaires completed by patients should be done first before the investigator assessments. Refer to [Section 6.2](#)
7. Only applicable for women of childbearing potential. Urine pregnancy tests will be performed at all visits indicated in the [Flow Chart](#). Urine pregnancy testing should be done prior to administration of study drug. Study drug should only be administered in case of a negative test result. In case of a positive urine pregnancy test, a serum pregnancy test will be performed at the central laboratory.
8. Complete Physical Examination (PE) includes general appearance as well as evaluation of all organ systems.
9. Targeted physical examination includes evaluation of organ systems associated with AE(s) symptoms or laboratory abnormalities.
10. Vital signs will be assessed pre dose as well as within 1 hour post dose.
11. Safety laboratory tests include clinical chemistry, haematology, coagulation, and urinalysis, and will be performed centrally. Where possible, safety laboratory tests are to be drawn prior to dosing.

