3.3.4.1 Discontinuation of trial treatment

An individual patient will discontinue trial treatment if:

- The patient wants to discontinue trial treatment, without the need to justify the decision.
- The patient has repeatedly shown to be non-compliant with important trial procedures and, in the opinion of both, the investigator and sponsor representative, is not willing or able to adhere to the trial requirements in the future.
- The patient misses more than 3 consecutive doses of trial treatment.
- The patient is unable to discontinue use of a restricted medication ([Section 4.2.2.1](#)) or requires other concomitant therapy that in the opinion of the investigator may interfere with trial treatment.
- The patient requires rescue medication for the treatment of unstable or worsening of AD. Refer to [Section 4.2.2.1](#)
- The patient can no longer receive trial treatment for medical reasons (such as surgery, adverse events, and other diseases.) For individual stopping rules related to specific adverse events, please see [Section 4.2.1](#) other treatments and emergency procedures.
- Malignancies during the trial. Refer to [Section 4.2.1](#)
- Severe, progressive, or uncontrolled hepatic disease during trial.
- The patient becomes pregnant during the trial.
- Confirmed active tuberculosis during the trial.
- The patient tests positive for HIV or Hepatitis B or C during the trial.

If a patient permanently discontinues trial treatment, the patient should return for the end of treatment (EOT) procedures as well as the end of study (EOS) procedures as outlined in the [Flow Chart](#) and [Section 6.2.3](#).

Discontinuation due to pregnancy

If a patient becomes pregnant during the trial the investigator must follow the AE reporting procedure as noted in [Section 5.2.6.2.3](#). The patient must discontinue drug and perform EOT and EOS procedures accordingly. The patient will be followed up until birth or otherwise termination of the pregnancy.

The data of the patient will be collected and reported in the clinical trial report (CTR) until last patient last visit (LPLV) and that any events thereafter will be reported in the BI Pharmacovigilance database.

It is per the Investigator opinion and judgment when trial medication can be temporarily interrupted and then reinstated for certain medical reasons such as surgery, adverse events

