Rescue medication is defined as the use of highly potent topical corticosteroids, systemic immunomodulating treatments or biologics for the treatment of unstable or worsening of AD. The use of the rescue medication leads to the discontinuation of the trial treatment.

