6.2.2 Treatment period

After Visit 1, the patient will return for 51 additional visits during the treatment period. The duration between visits is 4 weeks. At every visit study drug will be administered.

If the patient completes this 4 year study, the last study drug administration will be at Visit 52 (EOT).

Drug administration and rules for early/late visits

It's important for the patient to adhere to the visit schedule per the [Flow Chart](#). The visit schedule should always align with Visit 1.

The IRT system has been set up to make sure that a patient does not receive 2 doses of medication in less than a 14 day period.

In these scenarios, the patient should conduct the visit but skip the dose. The patient should be administered the dose at the next scheduled visit.

Pregnancy Testing

Urine pregnancy testing for all woman of childbearing potential will be conducted on-site prior to every dosing and must be negative to receive study drug. A positive urine test must be confirmed with a serum pregnancy test at the central laboratory.

See the [Flow Chart](#) for details of all procedures required at each visit.

Unscheduled visits

If a patient suspects that their AD is worsening in between the protocol specified scheduled visits, they should make an unscheduled visit and return to the clinic/site for assessment. The patient may be called in for additional unscheduled visits due to safety reason at the discretion of the investigator or the sponsor, unless the patient has withdrawn his/her consent. The patient may also contact the site due to safety reason for an unscheduled visit. The unscheduled visit may include additional collection of blood samples for safety reasons. The unscheduled visit may also include additional assessments deemed necessary by the investigator such as laboratory samples, ECGs, or other procedures which were missed at a previous visit. All unscheduled visits should be described (including the reason for the visit) and documented in the medical/source record, and in the eCRF.

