6. GENERAL ANALYSIS DEFINITIONS

6.1 TREATMENT(S)

For basic study information on the treatment to be administered, assignment to treatment, and selection of dose, cf. Section 4 of the CTP.

All patients will receive subcutaneous doses of 600 mg of BI 655130 solution for SC injection (every four weeks).

The following trial phases are defined:

Table 6.1: 1 Flow chart of trial phases

Trial phase	Description	Start (included)	End (excluded)
Open label Treatment phase	On-treatment period	Date of start of injection of first study drug (Day 1)	EoT visit date + 1 day
Follow-up phase	Off-treatment follow-up period	EoT visit date + 1 day	Date of EoS Participation visit + 1 day

Dates are defined individually per patient. If more than one date is associated with a specific visit, measurements associated with a specific date are assigned to a study analysis phase according to the rules specified in the table. An analysis phase will not extend beyond the start date of the following phase.

EoT = End of treatment; EoS = End of study;

Patients who discontinue the treatment but will continue on trial visits will be included in analyses with the available data. For patients who discontinue the trial prematurely only available data will be used in the analyses.

The time windows for data presentation in the analysis are described in [Table 6.7: 1](#).

Treatment group will be labelled as follows: "**Speso 600 mg SC q4w**" (i.e., patients receiving BI 655130 600 mg). In addition, the descriptive statistics will be presented for the following groups:

- By treatment received in the parent trial (1368-0032):
 - "Placebo" followed by "Speso 600 mg SC q4w"** – patients who were randomised to receive placebo in the double-blind period of the parent trial and received Speso treatment in the open-label period of the parent trial
 - "Placebo" followed by "no Speso 600 mg SC q4w"** – patients who were randomised to receive placebo in the double-blind period of the parent trial and

didn't receive Speso treatment in the open-label period of the parent trial (but didn't discontinue the parent study prematurely)

- **"Speso 600 mg SC q4w" followed by "Speso 600 mg SC q4w"** – patients who were randomised to receive active treatment (Speso) in the double-blind period of the parent trial and received Speso treatment in the open-label period of the parent trial

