6.6.3 Safety data

From CTP Section 7.5: *With respect to safety evaluations, it is not planned to impute missing values.*

The only exceptions where imputation might be necessary for safety evaluation are AE dates and start and stop dates for concomitant medications. Missing or incomplete AE dates are imputed according to BI standards (see BI-KMED-BDS-HTG-0035 (3)).

Partial start and stop dates for concomitant medications will be imputed to enable subsequent calculation (but not for display) by the following "worst case" approach:

- If the day of the end date is missing, then the end date is set to last day of the month (or to the patient's trial completion date, if it is earlier than the last day of the month).
- If the day and month of the end date are missing then the end date is set to 31st of December of the year (or to the patient's trial completion date, if it is earlier than the 31st of December of the year).
- If the day of the start date is missing the start date is set to first day of the month.
- If the day and month of the start date are missing then the start date is set to 1st January of the year.
- All other cases need to be assessed by the trial team on an individual basis, using the above points as guidance.

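### SAP 6.6.2 dates the non-response cut-off from the last dose, so in a narrow set of cases a Week-48 score taken after rescue has begun can count as a response

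*SAP*

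**What the plan says.** **Rescue stops trial drug.** Protocol 3.3.4.1 lists among the reasons for discontinuing: "The patient requires rescue medication for the treatment of unstable or worsening of AD". Protocol 4.2.2.1 defines rescue as highly potent topical corticosteroids, systemic immunomodulators or biologics given for unstable or worsening disease, and adds: "The use of the rescue medication leads to the discontinuation of the trial treatment".

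**Non-responder imputation (NRI) is tied to the last dose.** SAP 6.6.2 makes NRI the primary approach for binary endpoints. After premature discontinuation for any reason, later data are treated as missing, and "The cut-off date to be used is the last dose of study medication administration + 4 weeks (including the extended time windows". A missing outcome is a non-response, unless there are data on both sides: "then impute as success (a responder) only if both neighbouring visits also represent a success".

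**Scores can still be recorded after rescue starts.**
- Protocol 6.2.2: "If a patient suspects that their AD is worsening in between the protocol specified scheduled visits, they should make an unscheduled visit".
- Flow Chart footnote 6, on the efficacy assessments: "All assessments must be done prior to trial drug administration". A Week-48 score therefore does not depend on a Week-48 dose.
- SAP 6.1: "Patients who discontinue the treatment but will continue on trial visits will be included in analyses with the available data".
- SAP 6.7 assigns scheduled, repeated and unscheduled measurements to visits by date. Within a window it takes the value nearest the planned day, and the later one in a tie.

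Neither Protocol 7.3 nor the available SAP text has a rule specific to rescue.

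**The concern.** NRI is the conservative analysis of EASI50, EASI75 and the 2-grade IGA response. A patient who needs rescue has worsened on the study drug, and the protocol treats this as a reason to stop that drug. If the Week-48 score was taken while another active treatment was working, and it meets the response definition, the SAP reports it as a response in a table about BI 655130. With a single arm, no comparison group would show that this had happened. The results are also split by parent-trial treatment and by Week-16 response, where one patient weighs more than in the total.

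**Working it through.** **Inputs.** Planned days and extended windows: SAP Table 6.7:1. Cut-off: SAP 6.6.2. Sample size of about 40, at most 45: Protocol 7.5. Percentages use the whole patient set as denominator: SAP 7.

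1. *Reproduce the visit days.* Planned day = 7 × week + 1.
   - Week 44: 7 × 44 + 1 = 309. Week 48: 7 × 48 + 1 = 337. Both match the table.
   - 337 ± 14 = 323 to 351. The table starts Week 48 at Day 324 because Day 323 belongs to Week 44.

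2. *Cut-off after an on-time Week-44 last dose.*
   - Plain reading: 309 + 28 = Day 337.
   - Adding the 14-day window: 337 + 14 = Day 351.
   - The SAP does not say exactly how the extended windows enter, so both readings are carried.

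3. *Week-48 window days on which a score is kept.*
   - Plain: 337 − 324 + 1 = 14 of 28 days.
   - With the window: 351 − 324 + 1 = 28 of 28 days.
   - A late Week-44 dose on Day 323 gives 323 + 28 = 351, so all 28 days are kept even on the plain reading.

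4. *Time on rescue at a Day-337 score.* Rescue started on Day 310 gives 337 − 310 = 27 days; started on Day 336, 337 − 336 = 1 day. The score is kept in every case.

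5. *Where the gap ends.*
   - On-time Week-40 last dose (Day 281): cut-off 281 + 28 = 309, or 281 + 42 = 323. Both precede Day 324, so Week 48 is already missing.
   - Earliest last dose that leaves any Week-48 score: 324 − 28 = Day 296, or 324 − 42 = Day 282 with the window added.
   - A post-rescue score on Days 310 to 323 maps to Week 44. With no Week-48 score and no qualifying later visit, Week 48 is imputed as non-response.

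6. *Size per patient counted as a responder.* 1/40 = 2.5 points; 1/45 = 2.2 points. The number of such patients is an assumption: for 0 to 3, the range is 0 to 7.5 points at N=40 (3/40) and 0 to 6.7 at N=45 (3/45).

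7. *Order of steps in a fix.* Take the Day-351 cut-off, a pre-rescue response on Day 330 and a post-rescue non-response on Day 344. Both lie 7 days from Day 337, so SAP 6.7 selects Day 344: non-response.
   - If post-rescue scores were dropped before selection, Day 330 would be used and the patient would become a responder.
   - If selection comes first and the rescue rule second, the outcome stays non-response.

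   Only the second order guarantees that the change cannot raise the rate.

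**The case against.** **The discontinuation pathway closes most of the gap.** A patient who stops goes to the end-of-treatment (EOT) visit as soon as possible and then to the end-of-study visit 16 weeks after the last dose (Flow Chart footnote 4, Protocol 6.2.3). A prompt EOT visit before Day 324 falls in Week 44. An EOT score taken before rescue is given is a legitimate pre-rescue score. This stands and limits the finding. The gap remains for a V13, EOT or unscheduled score on Days 324 to 337 (or 351).

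**Some inputs cannot be seen.** The EOT procedure table is not in the available text, and Protocol 6.2.2 does not require EASI or IGA at unscheduled visits. So it cannot be confirmed how often a stopping patient is scored in the window. This also stands. Any score that is recorded would be assigned by date.

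**SAP 6.6.2 speaks of data after the discontinuation, which might suggest an earlier cut-off.** The next sentence fixes the date at last dose + 4 weeks, so this does not close the gap.

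**One dosing interval is a coherent rule, and rescue as failure is an estimand preference.** That is fair for discontinuation in general. For rescue, however, the retained score reflects another treatment, which sits badly with the NRI approach that the SAP itself chose.

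**The combination is demanding.** The patient must worsen enough to need rescue and then meet a response definition within weeks. This is hardest against the extension baseline, which follows a response in the parent trial. This supports a small expected number.

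**Readings that go too far.** A reader might infer that rescued patients are routinely counted as responders, or that any rescue rule must lower the rate. The first ignores the EOT pathway and step 5; the second fails under step 7. A reader might also fault the continuous summaries and observed-data tables, but as-observed reporting there is a stated choice.

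**Conclusion.** The point holds as a minor one. After a Week-44 last dose, the NRI rule keeps an EASI or IGA score taken on rescue in the Week-48 window up to Day 337, or Day 351 with the window added, and such a score can be reported as a response. All three binary endpoints and both baseline analyses are exposed.

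The size is 2.5 points per such patient at N=40 and 2.2 at N=45. These figures are one patient divided by the set size and say nothing about frequency. With no rescue rate in the documents, the number is unknown and probably small, and could be zero. A reader might infer large distortions in the parent-treatment groups; their sizes are not given, so any such figure would rest on an assumed split.

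The analysis is secondary and descriptive, with no hypothesis test, so no error rate is affected. The conclusion assumes that the unseen dataset specifications contain no rescue rule.

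**What to change.** Add to SAP 6.6.2, for the NRI analysis of EASI50, EASI75 and IGA response:

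1. Select the visit value first, by the existing SAP 6.7 rule.
2. If the selected score was taken after the start of rescue medication as defined in Protocol 4.2.2.1, the outcome is non-response, even within last dose + 4 weeks, and the neighbouring-visit rule does not reverse it.
3. A score on the day rescue starts counts as pre-rescue unless recorded times show otherwise.
4. Rescue is identified from the concomitant-therapy records, by indication and medical review, before database lock. A simple drug flag is not enough: rescue differs from restricted medication by indication and, for topical steroids, also depends on potency.

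In this order the change can only lower the NRI rate or leave it unchanged. Leave the observed-data tables and continuous summaries as they are. A separate rule for partial rescue dates would be more than so narrow a gap needs.

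The cost is a few SAP sentences, a little programming, a small medical review and possibly slightly lower response rates. No change to clinical management is proposed.

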1.4.2 Risks

There are no identified or potential safety risks for BI 655130, based on the toxicology programme or any clinical trials conducted for this product to date (Refer to [Section 1.2](#)). No other IL-36 receptor antagonist is currently approved, providing information on identified risks in molecules of this class.

Currently there are no data available to suggest interactions of BI 655130 with other drugs [[c03320877-06](#)]. Since the drug exposure in this trial is expected to be lower than in the parent trial (1368-0032), there is a risk that some patients will lose response. Rules for discontinuation for these patients are outlined in [Section 3.3.4.1](#).

The risks shown in the table below are hypothetical in nature; these are derived from general safety considerations of immunomodulatory drugs.

In order to protect the patient's safety during conduct of this trial, an independent Data Monitoring Committee has been established for the periodic review of clinical trial safety data.

Table 1.4.2:1 Study Risks

Hypothetical risks of clinical relevance for this trial	Summary of data, rationale for the risk	Mitigation strategy
Investigational Medicinal Product		
Drug Induced Liver Injury (DILI)	Rare but severe event, thus under constant surveillance by sponsors and regulators.	Timely detection, evaluation, and follow-up of laboratory alterations in selected liver laboratory parameters to ensure patients' safety. See Section 5.2.6 (AESI)

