7.3 HANDLING OF MISSING DATA

Every effort will be made to collect complete data at all visits. However, missing data will still occur and approaches to handle this are proposed below.

With respect to safety or continuous efficacy evaluations, it is not planned to impute missing values.

For all binary endpoints (i.e. endpoints that are either 1 (patient responded) or 0 (patient did not respond)), the following rules apply:

- If there are data at visits both before and after the visit with a missing outcome, then impute as responder only if both neighbouring visits also represent a responder;
- Otherwise, impute as a non-responder.

For disease specific protein markers the following handling of data below or above the limit of quantification will be applied:

- Below limit of quantification (BLQ) data will be replaced by 0.5 times the lower limit of the quantification (LLOQ)
- Above limit of quantification (ALQ) data will be replaced by upper limit of quantification (ULOQ), if ULOQs are available. Otherwise, ALQ data will be excluded from the analysis.

Further sensitivity analyses to assess the robustness of the results may be performed and as such will be described in the TSAP.

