7.5 SECONDARY ENDPOINT(S)

7.5.1 Key secondary endpoint(s)

[figure not shown]
This section is not applicable as no key secondary endpoint has been specified.

7.5.2 (Other) Secondary endpoint(s)

All secondary efficacy endpoints will be analysed descriptively based on the FAS.

For continuous secondary efficacy endpoints (EASI Score and SCORAD Score), standard statistical parameters (as defined in [Section 7](#)) will be presented per group defined in [Section 6.1](#). Both absolute and percent change from baseline will be analysed as an outcome as well as the values recorded at the respective time points.

For binary endpoints (EASI50, EASI75, achieving at least 2-grade reduction from baseline to clear (0) or almost clear (1) in IGA), frequency tables will be provided per group defined in [Section 6.1](#).

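### Week-48 EASI and SCORAD means use observed values only, so they describe mainly patients still on treatment without rescue and may overstate how well improvement is maintained

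*SAP*

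**What the plan says.** **Missing data.** SAP 6.6.2: "For efficacy endpoints which are continuous in nature, no imputation of missing data is planned. Only observed data will be used for analysis". Protocol 7.3 agrees: "With respect to safety or continuous efficacy evaluations, it is not planned to impute missing values". SAP 7.5.2 names the endpoints affected: "For continuous secondary efficacy endpoints (EASI Score and SCORAD Score), standard statistical parameters" are to be shown by group, for absolute and percent change and for the values themselves.

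**Rescue.** Protocol 3.3.4.1 lists as a reason to stop treatment: "The patient requires rescue medication for the treatment of unstable or worsening of AD". Protocol 4.2.2.1 repeats it: "The use of the rescue medication leads to the discontinuation of the trial treatment".

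**Visits after stopping.** Flow Chart footnote 4 covers all dosed patients, "including those who discontinue treatment prematurely, should complete the EOT visit as soon as possible and complete the EOS visit 16 weeks after" the last dose. Protocol 6.2.3 says the same. Neither asks for the remaining scheduled visits.

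**Expected course.** Protocol 1.4.2: "Since the drug exposure in this trial is expected to be lower than in the parent trial", "there is a risk that some patients will lose response". It then refers to the discontinuation rules for these patients.

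**Binary endpoints.** For EASI50, EASI75 and the IGA response, SAP 6.6.2 treats data later than the last dose plus 4 weeks as missing after early discontinuation. It counts missing outcomes as non-response, apart from gaps between two responding visits, and it also tabulates observed data. The cut-off appears only under binary endpoints. SAP 6.1 keeps whatever data are available after treatment stops.

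**Sensitivity analyses.** SAP Section 5 refers to Section 6.6 for them, and Protocol 7.3 leaves them optional. The SAP text available gives none for continuous endpoints.

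**The concern.** A patient who worsens enough to be rescued stops treatment and, in most cases, has no EASI or SCORAD near Week 48. That patient leaves the mean for a reason tied to the outcome being averaged. Those who remain are a selected group, and their mean cannot show what happened to the others.

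Efficacy is part of the stated primary objective (Protocol 2.1.1). Whether response holds at the lower exposure is a question the protocol itself raises. Status reviews are meant to feed regulatory interactions, investigator brochure updates and publications (Protocol 7.2.7). A Week-48 mean read as the result for the treated group could mislead in those uses. Two of the five secondary endpoints are affected.

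**Working it through.** The plan gives no dropout rate, rescue rate, SD or sample size calculation, so there is no figure to reproduce. Three checks can be made.

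**1. Who can contribute a Week-48 value after stopping early?**

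Inputs:
- Doses fall on Day 1 + 28k, where k = 0 to 11 covers Weeks 0 to 44 (Flow Chart).
- EOS falls 112 days after the last dose (Flow Chart footnote 4).
- The Week-48 window is Day 324 to 351 (SAP Table 6.7:1).
- Assumption: EOT takes place 1 to 28 days after the last dose.

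EOS day = 1 + 28k + 112 = 113 + 28k. It lies in 324 to 351 only if 211 ≤ 28k ≤ 238, so k = 8: last dose Week 32 (Day 225), EOS Day 337.

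EOT range = Day 2 + 28k to Day 29 + 28k. It reaches Day 324 only if 28k ≥ 295, so k = 11: last dose Week 44 (Day 309), EOT Day 310 to 337.

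Two of the 12 possible last doses can therefore place a value in the window, and ten cannot. Even those two depend on EASI and SCORAD being taken at EOT or EOS. The flow chart for those visits is not in the text available, so this cannot be confirmed.

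If they are taken, both values could follow rescue. Extending the binary cut-off would remove the first, since Day 337 is 112 days after the last dose. It would not remove the second, which lies within 28 days of the last dose. A separate rule on rescue is needed for that one.

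**2. How large could the overstatement be?**

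Let f be the fraction missing, S the mean improvement in stayers and L that in leavers.

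All-patient mean = (1 − f)S + fL, so overstatement = S − [(1 − f)S + fL] = f × (S − L).

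The values of f, S and L are assumptions. Take S = 75% and N = 40 (Protocol 7.5 plans about 40):

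| Missing | L = 50% | L = 25% | L = 0% |
|---|---|---|---|
| 10% (4 of 40) | 2.5 points | 5 points | 7.5 points |
| 20% (8 of 40) | 5 points | 10 points | 15 points |
| 30% (12 of 40) | 7.5 points | 15 points | 22.5 points |

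The observed mean is 75% in every cell. With L = 25%, the all-patient mean is 70%, 65% and 60%.

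This counts every leaver as a poorer case. Suppose instead that half left for administrative reasons and are excluded. The fraction becomes (f/2)/(1 − f/2), and with a 50-point difference the gap is:
- 10% missing: 0.05/0.95 × 50 = 2.6 points
- 20% missing: 0.10/0.90 × 50 = 5.6 points
- 30% missing: 0.15/0.85 × 50 = 8.8 points

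For contrast, take an assumed EASI75 rate of 70% among stayers. Counting leavers as non-responders gives 0.70 × (1 − f) = 63%, 56% and 49%.

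**3. How recent is the last pre-rescue value?**

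Scheduled EASI and SCORAD in Year 1 fall at Visit 1 and Weeks 12, 24, 36 and 48 (Flow Chart). The last scheduled value before rescue can be up to about 12 weeks old and may predate the worsening.

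**The case against.** A reader might infer that everyone who loses response leaves the mean, so that it must look stable while response is being lost. The documents do not support that. Rescue is at the investigator's discretion (Protocol 4.2.1 and 4.2.2.1), and Protocol 3.3.4.1 sets no EASI threshold for stopping. A patient who loses response without rescue stays on treatment, is scored, and pulls the mean down. Patients also leave for reasons unrelated to efficacy. The accurate description of those who remain is still on treatment without rescue, which is not the same as still doing well.

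A reader might also infer that the failures are hidden. They are not. Three of the five secondary endpoints count early stoppers as non-responders, and the observed binary tables beside them show the effect of dropout. The number of non-missing values accompanies each continuous summary, discontinuations are reported by reason, and earlier visits are analysed. What these do not show is why a given patient is absent from the Week-48 mean, or how far the mean would move if that patient were counted.

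The trial is single-arm and descriptive, its primary endpoint is safety, and there are no key secondary endpoints. This limits the consequence to interpretation; no error rate is at stake. The objection on carry-forward also stands: a pre-rescue value can be stale and still optimistic, so it is not enough alone.

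**Conclusion.** The point holds in this form: the Week-48 EASI and SCORAD means describe mainly patients still on treatment without rescue. They will tend to overstate maintained improvement if those who left did worse. The direction depends on that condition, which is plausible because rescue for worsening is itself a reason to leave.

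The size cannot be determined from the documents. The 5 to 15 points at 10% to 30% missing rest on an assumed 50-point difference and on all leavers being poorer cases. They are an illustration, not an estimate. They also suit the parent-trial baseline better than the extension baseline, because patients enter having already responded.

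A second gap stands beside it: nothing in the SAP text available keeps a post-rescue EOT or EOS value out of the continuous summaries, if EASI and SCORAD are taken at those visits. The change is worth making because a stated rule creates the selection and the remedy is cheap.

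**What to change.** 1. Keep the observed-data table as planned, but apply the last-dose-plus-4-weeks cut-off to continuous endpoints and set values after rescue to missing. Align the SAP 6.1 sentence on data after discontinuation with this.
2. Add a supportive Week-48 row for EASI and SCORAD, for each of the two baselines. Patients who stopped for rescue, lack of effect or an adverse event contribute their last on-treatment value before rescue. Administrative stops are not imputed.
3. Add a less favourable bound, because that value may predate the worsening: either the worst on-treatment value or no improvement from baseline. If the second is used, it should mean return to the parent-trial baseline score in both analyses. Zero change from the extension baseline would mean that response was kept.
4. Beside each mean show the number observed, the number imputed and the reasons for missingness. Also state how many treated patients fall outside the FAS for want of a post-baseline EASI, since these rows do not include them.

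Cost: a few SAP sentences and two extra rows per table. Protocol 7.3 already allows further sensitivity analyses to be described in the SAP. The downside is that single imputation is approximate and its SD should not be over-read.
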